6.4.1.2. Main Analysis Approach

Clopper-Pearson method will be used to summarize 95% CI of proportion of clinical cure for group A and group B separately. Pairwise treatment comparison of subjects in group B 3 days vs. subjects in group B 7 days will be performed to test primary efficacy endpoint (clinical cure at TOC visit) using a Fisher's Exact

test; p-values and 95% confidence intervals for odds ratio will be presented. The primary endpoint will also be analyzed of subjects in group B 3 days vs. subjects in group B 7 days using a Cochran-Mantel-Haenszel row mean scores test stratified by site.

VSS scores at Baseline, TOC, and FU will be summarized for each sign and symptom using frequency counts and percentages.

Summary statistics will be provided for the total VSS composite score (observed value and change from baseline). Student's t-test will be used for pairwise treatment comparison of subjects in group B 3 days vs. subjects in group B 7 days; p-values and 95% confidence intervals will be presented for the differences between treatment groups.

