11.1. Inclusion Criteria

Subjects must fulfill all of the following criteria to be eligible for study admission:

- 1) Subject is a post menarchal female ≥ 18 years of age at the time of signing the ICF.
- 2) Subject has a diagnosis of symptomatic VVC that meets the following criteria at the Screening visit:
 - a) Minimum composite vulvovaginal signs and symptoms score of ≥ 4 with at least 2 signs or symptoms having a score of 2 (moderate) or greater on the VSS scale at baseline.
 - b) Positive microscopic examination with 10% KOH in a vaginal sample collected at Screening revealing yeast forms (hyphae/pseudohyphae) or budding yeasts
 - c) Normal vaginal pH (≤ 4.5).
 - d) Has no other vaginal co-infections based on WET Mount microscopic examination (and/or DNA probe).
- 3) Subject should also have:
 - a) A VVC with persistent symptoms despite fluconazole therapy (last dose of fluconazole must have been administered at least 7 days prior, but no longer than 28 days prior to screening).

OR

b) A recurrent vulvovaginal candidiasis (RVVC) episode with breakthrough symptoms while receiving maintenance antifungal therapy.

OR

c) A VVC episode caused by a non-*albicans candida species* known to have either intrinsic resistance to fluconazole e.g. *C.krusei* or suspected resistance to fluconazole, e.g. *C.glabrata*, *C auris* but likely without MIC data in hand.

OR

d) A VVC episode caused by *candida* species with documented resistance to fluconazole based on MIC determination.

OR

e) A known history of azole allergy or intolerance.

4) Subject is able to take oral tablets.

5) Subject is not pregnant or lactating and plans not to become pregnant. Women of childbearing potential < 1 year post-menopausal must agree to and comply with using one barrier method (male condom, female condom, and diaphragm) plus one other highly effective method of birth control, or sexual abstinence, from the time of consent through 10 days after the completion of study therapy. **Subjects must refrain from using any topical vaginal contraceptives as these may have an impact on the signs and symptoms of VVC.**

Note: Women of childbearing potential must have a negative urine pregnancy test prior to enrollment (performed by the site's local laboratory).

6) Subject is able to understand and sign a written ICF, which must be obtained prior to treatment and any study-related procedures.

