5.4. Sample Size

This is an exploratory study, and no formal sample size calculation was performed. Approximately 150 subjects will be enrolled in allocation 50:50:50 in respect of 1, 3 and 7 days of treatment. Subjects will be randomized to treatment, stratified by group based on the *Candida* species and presence or absence of underlying conditions. The sample size of 150 is estimated to be adequate to perform an initial assessment of efficacy.

6. Statistical Analyses

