6.1. General Considerations

All statistical processing will be performed using SAS® version 9.3 or later, unless otherwise stated. All statistical tests will be two-sided and interpreted at a 5% significance level.

The study is not powered for formal statistical comparisons. Descriptive statistics (i.e., mean, standard deviation, median, minimum, maximum, etc.) will be provided for all continuous variables; frequencies and percentages will be tabulated for incidence and categorical variables. For parameters measured over time, observed values and changes from baseline will be described for each time point.

The clinical cure and mycological eradication rates will be described by baseline Candida species, when the number of isolates per species allows.

All analyses will be presented by treatment group. Unless otherwise stated, data will be analyzed as it is with no imputation. No adjustment for multiplicity will be employed.

This Statistical Analysis Plan (SAP) will describe all statistical analyses in detail. The SAP will be finalized prior to database lock.

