6.1.1. Baseline and Change from Baseline Definition

Baseline is defined as the last assessment prior to the first dose of study drug. If time and date are available, then the baseline assessment could be on the same day as first dose so long as it's before the time of first dose. If time is not available, the date prior to first dose will need to be used. Change from baseline is defined as: non-missing post- baseline value – baseline value. Baseline values will be re-calculated in Cycle 2 for QOL scale, VVS composite score, physical examinations, lab results and vital signs. If above baseline value is not available in Cycle 2, then use the last available value in Cycle 1 as baseline for Cycle 2.

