6.3.6. Study Drug Administration

Treatment Cycle 1: All randomized subjects

Subjects who meet all the inclusion and none of the exclusion criteria will be randomized to treatment and stratified into 2 groups based on the Candida species and presence or absence of underlying conditions. Subjects will receive open-label oral ibrexafungerp 300 mg BID for one, three or seven consecutive days per [TABLE 1](#):

| Treatment Group | Criteria | Ibrexafungerp Dose Randomization and Stratification |
|-----------------|---|---|
| Group A | Subjects without underlying medical conditions AND known to have isolates other than C glabrata, C krusei, C auris | 1 Day dosing (300mg AM and 300mg PM) N = 50 |
| Group B | Subjects with underlying medical conditions: DM, immunocompromised conditions (e.g. HIV), debilitation, immunosuppressive therapy (e.g. corticosteroids), recurrent VVC (≥ 3 episodes/year) AND/OR known to have C glabrata, C krusei or C auris isolates | 3 Days or 7 Days dosing (300mg AM and 300mg PM) Randomized 1:1 N = 50:50 |

6.4. Efficacy Analyses Cycle 1

The efficacy analyses will be conducted using the MITT (primary analysis population), ITT and PP populations to evaluate ibrexafungerp. Efficacy outcomes will be presented by treatment group in Cycle 1.

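### The 3- versus 7-day comparison of clinical cure has two unranked tests, neither adjusted for baseline VSS, and no confidence interval for the difference in cure rates

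*SAP*

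**What the plan says.** The treatment table in SAP 6.3.6 assigns Group A to one day by criteria. Only Group B is randomised: "Randomized 1:1 N = 50:50", to 3 or 7 days.

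For clinical cure at TOC, SAP 6.4.1.2 plans three things:

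- Clopper-Pearson intervals for Group A and Group B separately.
- A 3- versus 7-day comparison in Group B, "performed to test primary efficacy endpoint (clinical cure at TOC visit) using a Fisher's Exact" test, with p-values and a confidence interval for the odds ratio.
- A further comparison of the same two arms on the same endpoint, "using a Cochran-Mantel-Haenszel row mean scores test stratified by site".

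It ranks neither test above the other. For the total VSS score, the same section plans confidence intervals for differences between the arms; for cure it does not.

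Cure means a composite VSS of 0. Entry requires a "Minimum composite vulvovaginal signs and symptoms score of ≥ 4 with at least 2 signs or symptoms having a score of 2" or more (Protocol 11.1). The scale has six items scored 0 to 3, so the entry score runs from 4 to 18. The SAP summarises baseline VSS, but neither test of cure uses it.

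SAP 6.1 sets the reading rule, "All statistical tests will be two-sided and interpreted at a 5% significance level", and adds: "The study is not powered for formal statistical comparisons". SAP 5.4 says: "This is an exploratory study, and no formal sample size calculation was performed".

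**The concern.** A woman who enters with a score of 15 plausibly has further to go to reach 0 than one who enters at 4. If so, baseline VSS predicts cure. Leaving it out then widens the interval and exposes the estimate to chance imbalance in severity between two small arms. The primary population is MITT (culture-positive), so the arms may be smaller than 50.

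Fisher's exact test is also conservative at this size, so part of the stated 5% goes unused. With two tests and no ranking, the two p-values can fall on either side of 5% with no rule for which to report. Finally, a reader choosing between durations wants the difference in cure rates with its precision, and the plan supplies an interval only for the odds ratio.

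**Working it through.** The documents give no power, effect size or calculated sample size, so there is no stated figure to reproduce.

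**Inputs**

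- Two-sided 5% level (SAP 6.1); 50 per arm randomised (SAP 6.3.6).
- MITT share: 188 of 298 treated in the second earlier phase 3 trial (Protocol 7.1.4), 188/298 = 0.63. Carrying this over is an assumption: 0.63 × 50 ≈ 32 per arm.
- Cure of 50.5% and 63.3% in the two earlier acute-VVC trials (Protocol 7.1.4), used only as anchors.
- Assumed, with no source in the documents: the true 3- versus 7-day difference and the association of baseline VSS with cure.

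**Real size of Fisher's test.** Sum Bin(a; n, p) × Bin(b; n, p) over all tables (a, b) whose two-sided Fisher p-value is at most 0.05.

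| n per arm | p = 0.505 | p = 0.633 |
|---|---|---|
| 50 | 0.035 | 0.031 |
| 32 | 0.033 | 0.029 |

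**Size of the CMH test.** Simulated at 50 per arm with 5 to 30 equal-chance sites and no site effect: 0.049 to 0.053. Protocol 10.4 does not give the number of centres.

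**Power, CMH minus Fisher,** at 50 per arm (40% vs 60%, and 50% vs 75%):

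| Sites | Change in points |
|---|---|
| 5 | about +4 to +5 |
| 10 | about +1.5 to +2.5 |
| 20 | about −2 to −2.5 |
| 30 | about −7 to −8 |

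With many small sites the CMH test can therefore be the weaker of the two.

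**Adjusted risk difference against Fisher.** Linear regression of cure (0/1) on treatment and baseline VSS with HC3 errors, simulated at an assumed 50.5% vs 75.5%; Fisher power is exact.

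| n per arm | Fisher | Adjusted, OR 1 per SD | Adjusted, OR 3 per SD | Gain in points |
|---|---|---|---|---|
| 50 | 0.677 | 0.73 | 0.82 | 5 to 14 |
| 32 | 0.462 | 0.54 | 0.60 | 8 to 14 |

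The adjusted test's simulated size was 0.043 to 0.054. A repeat simulation agreed to within a point or two.

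**How much comes from dropping Fisher alone.** Exact power at 50 per arm for 50% vs 75% is 67.5% for Fisher and 74.5% for an uncorrected chi-square, or 7 points with no covariate. The chi-square's simulated size near 50% cure was 0.054 to 0.058, so part of that is a slightly liberal test.

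**Smaller difference.** Large-sample power ≈ Φ(d/SE − 1.96) + Φ(−d/SE − 1.96), with SE² = [p1(1−p1) + p2(1−p2)](1 − r²)/n, where r is the correlation of baseline VSS with cure. At n = 50:

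- 50.5% vs 60.5%, r = 0: SE = √(0.48895/50) = 0.0989; 0.10/0.0989 = 1.011; power 0.173.
- 50.5% vs 75.5%, r = 0: SE = √(0.43495/50) = 0.0933; 0.25/0.0933 = 2.680; power 0.764.

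| Cure rates | Fisher | r = 0 | r = 0.3 | r = 0.5 |
|---|---|---|---|---|
| 50.5% vs 60.5% | 0.134 | 0.173 | 0.185 | 0.215 |
| 50.5% vs 75.5% | 0.677 | 0.764 | 0.802 | 0.872 |

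For the 10-point difference the gain is 4 to 8 points, against 9 to 20 on the same large-sample basis for the 25-point difference. Power is poor either way.

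**The case against.** The strongest reply is that there is no power promise to break. The study is exploratory. Its primary objective is efficacy based on cure, not a comparison of durations. Protocol 18.6.2 makes the primary analysis a rate with a Clopper-Pearson interval and leaves other efficacy data without formal analysis. An exact test in small arms is a respectable choice. All of this stands, and it limits the weight of the point. It does not dispose of it: the SAP chose to test this contrast at 5% and report p-values, and small arms are a reason to use data already held.

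A reader might infer that the whole randomised comparison runs at about 3%. The documents do not support that, because the CMH test of the same endpoint and arms runs near 5%. The conservatism belongs to Fisher's result only.

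A reader might also infer a fixed loss of power, up to 14 points or more. That is not supported either. The 25-point difference between two active durations is assumed. So is the prognostic strength: an odds ratio of 3 per SD means a ninefold ratio of cure odds (3² = 9) between women two SDs apart. The anchor rates come from trials that excluded this population (Protocol 7.2.1).

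One practical objection also stands. Signs are rated at Screening, which may fall on Day 1. SAP 6.1.1 calls for an earlier date when no time is recorded, so some subjects could lack a baseline composite unless a rule is written.

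**Conclusion.** The point holds as a modest efficiency and pre-specification weakness. It is not a failed power claim, since none is made. Three parts rest on the documents alone: the SAP does not say which of its two tests of 3- versus 7-day cure governs, neither uses baseline VSS, and no interval is planned for the cure-rate difference. Fisher's real size of about 3% follows by exact calculation at the two earlier cure rates for 32 to 50 per arm; the 32 is an assumption.

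The gain is conditional. At an assumed 50.5% vs 75.5% it is about 5 to 8 points over Fisher with no prognostic value in baseline VSS, and about 14 points at an assumed odds ratio of 3 per SD. It shrinks in absolute terms for smaller differences. Against the CMH test it depends on a number of sites that the documents do not give.

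**What to change.** In SAP 6.4.1.2, before database lock, state:

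- **Main Group B comparison:** the 7-day minus 3-day difference in clinical cure at TOC, from a linear regression of cure (0/1) on treatment and baseline total composite VSS (continuous), with an HC3 robust 95% confidence interval and two-sided p-value.
- **Baseline rule:** the Screening/Day 1 pre-dose score, with same-day Screening scores counted as baseline.
- **Supportive analyses:** Fisher's exact test with the odds ratio, and the site-stratified CMH test.

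The Clopper-Pearson intervals stay as planned. The cost is a short SAP edit and one model on data already collected, with no added subjects or procedures. The downside is that the main estimate becomes model-adjusted and no longer reads straight off a 2×2 table, which is why the two planned tests are kept beside it.

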A second treatment cycle (Cycle 2) will be allowed for subjects who did not achieve sufficient clinical improvement (e.g. VSS remains ≥ 3) on the randomized treatment (Cycle 1) as evaluated at the TOC visit or at the FU EOT+14 visits. The same visit schedule will be followed, starting with the Baseline visit.

TARGET POPULATION: The study population will include female subjects who are ≥ 18 years of age with complicated VVC who have failed fluconazole therapy.

KEY INCLUSION CRITERIA:

Subjects must fulfill all the following **KEY** criteria at Screening (Day -2 (± 1)) to be eligible for study admission:

- 1) Subject is a post menarchal female ≥ 18 years of age at the time of signing the informed consent form (ICF).
- 2) Subject has a diagnosis of symptomatic VVC that meets the following criteria at the Screening visit:
 - a) Minimum composite vulvovaginal signs and symptoms score of ≥ 4 with at least 2 signs or symptoms having a score of 2 (moderate) or greater on the VVS scale at baseline.
 - b) Positive microscopic examination with 10% KOH in a vaginal sample collected at Screening revealing yeast forms (hyphae/pseudohyphae) or budding yeasts.
 - c) Normal vaginal pH (≤ 4.5).
 - d) Has no other vaginal co-infections based on WET Mount microscopic examination and/or DNA probe.
- 3) Subject should also have:

a) A VVC episode with persistence of symptoms despite fluconazole therapy (last dose of fluconazole must have been administered at least 7 days prior, but no longer than 28 days prior to screening).

OR

b) A recurrent vulvovaginal candidiasis (RVVC) episode with breakthrough symptoms while receiving maintenance antifungal therapy.

OR

c) A VVC episode caused by a *non-albicans candida species* known to have either intrinsic resistance to fluconazole e.g. *C.krusei* or suspected resistance to fluconazole, e.g. *C.glabrata*, *C auris* but likely without MIC data in hand.

OR

d) A VVC episode caused by a *candida* species with documented resistance to fluconazole based on MIC determination.

OR

e) A known history of azole allergy or intolerance.

4) Subject is able to take oral tablets.

KEY EXCLUSION CRITERIA:

A subject will be excluded from participation in the study if she meets any of the following **KEY** exclusion criteria:

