10.1.1. Study Visits

The study will consist of a Screening visit on Day -2 (± 1), Baseline visit on Day 1 (if applicable, the Screening and Baseline visits can both be done on Day 1), Phone contacts on Days 3, 5 and 7 (± 1), a TOC visit 14 (± 3) days after Baseline, FU visits at: 14 (± 3) days after EOT, 30 (± 4) after Baseline, 30 (± 4) after EOT and 60 (± 4) days after EOT.

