14.11. Rating of Vulvovaginal Signs by the Investigator Using the VSS Scale

The investigator (or qualified designee) will perform vulvovaginal examinations to rate the subject's signs of infection at the Screening, TOC and first FU visits at 14 days after EOT. The vulvovaginal examination will be repeated at the rest of the FU visits only if the subject presents with symptoms. Otherwise, no additional vulvovaginal examination will be conducted, or signs rated. Vulvovaginal examinations may be conducted at unscheduled visits, if needed.

If the subject experiences persistence or worsening or recurrence of symptoms that per the investigator's assessment (e.g. symptoms ≥ 4) warrant the use of rescue antifungal therapy, the subject may be enrolled into Treatment Cycle 2 and receive additional treatment with ibrexafungerp for a period up to 14 days as recommended by the investigator and following discussion with the sponsor.

Whether or not a subject enters Treatment Cycle 2, or be prescribed rescue therapy, a vaginal examination with rating of signs by the investigator should be completed prior to initiation of rescue therapy. If the investigator's rating of the vulvovaginal signs is not possible prior to the initiation of the rescue therapy, it should still be completed as soon as possible after rescue therapy is initiated.

Investigators will assess the signs of infection using the VSS Scale provided in Section 21 [Appendix 2]), a standardized, predefined scale where each sign of the vagina and/or vulva will be given a numerical rating based on severity, as follows:

- Edema: absent = 0; mild = 1; moderate = 2; severe = 3
- Erythema: absent = 0; mild = 1; moderate = 2; severe = 3
- Excoriation or fissures: absent = 0; mild = 1; moderate = 2; severe = 3

Other findings will be recorded using the most relevant medical term in the abbreviated physical examination page of the eCRF.

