4.2.2. Secondary Endpoints

Efficacy as measured by:

- The percentage of subjects with clinical improvement:
 - Total composite score of 2 on the VSS scale at the TOC and FU visits
 - Total composite score of 1 on the VSS scale at the TOC and FU visits.
- The percentage of subjects with total composite score equal or less than 2 and equal or less than 1 on the VSS scale at the TOC and FU visits.
- The percentage of subjects with clinical success (at least 50% reduction from baseline in the total composite VSS score) with no additional antifungal therapy required based on investigator's judgment) at the TOC and FU visits.
- The percentage of subjects with mycological response (defined as a negative culture for growth of *Candida spp.* or subject is asymptomatic, therefore culture not done) at the TOC and FU visits.
- The percentage of subjects with both clinical cure and mycological response at the TOC and FU visits.
- The percentage of subjects with clinical cure at the FU visits.
- The absolute change in total composite VSS score from baseline to the TOC and FU visits.

Exploratory Endpoints:

- Absolute improvement in QOL outcomes at TOC and FU visits compared to baseline as measured by QOL survey.
- Subjects whose signs and symptoms have resolved enough that additional antifungal treatment was not required based on clinical judgement.
- Time to resolution of symptoms.

Safety and Tolerability as measured by:

Adverse events (AEs), vital signs, treatment discontinuation, and safety laboratory tests.

5. Study Design

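### The randomised Group B 3- versus 7-day comparison of composite VSS ignores the baseline score and names neither scale nor visit; baseline-adjusted ANCOVA at TOC settles this without new data

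*SAP*

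**What the plan says.** Group A receives 1 day of treatment by its entry criteria. Group B is randomised 1:1 to 3 or 7 days, 50 per arm (SAP 6.3.6), so 3 versus 7 days is the only randomised comparison.

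On the composite score, SAP 6.4.1.2 first states "Summary statistics will be provided for the total VSS composite score (observed value and change from baseline", and then that a Student's "t-test will be used for pairwise treatment comparison of subjects in group B 3 days vs. subjects in group B 7 days", with p-values and 95% confidence intervals for the difference. SAP 4.2.2 lists as a secondary endpoint "The absolute change in total composite VSS score from baseline to the TOC and FU visits", and SAP 6.4.2.2 treats that endpoint descriptively. No baseline-adjusted model appears in either document.

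On baseline data, subjects rate symptoms at Screening and on Day 1 (Protocol 14.8). The investigator rates "signs of infection at the Screening, TOC and first FU visits at 14 days after EOT" (Protocol 14.11), so signs have one scheduled pre-dose rating. Protocol 10.1.1 allows that "the Screening and Baseline visits can both be done on Day 1". For the baseline value SAP 6.1.1 adds: "If time is not available, the date prior to first dose will need to be used".

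Clinical cure is compared by Fisher's exact test and then also "using a Cochran-Mantel-Haenszel row mean scores test stratified by site". SAP 5.3 gives *Candida* species and underlying conditions as the randomisation strata and does not mention site.

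**The concern.** Two different t-tests, one on the observed score and one on the change, both satisfy the sentence. They can give different estimates and p-values for the same question. The study is open-label and makes no multiplicity adjustment, so this choice should not stay open until results are visible.

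Neither test uses the baseline score in the best way. The observed-score test ignores it, and the change-score test in effect fixes its coefficient at 1. In a trial with no power calculation, discarding information already collected is a needless loss.

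The baseline itself is not secure. Its sign and symptom halves may come from different visits, and SAP 6.1.1 does not say whether they may be combined. A subject screened and dosed on the same day with no recorded times has, on a literal reading, no baseline composite. She would drop out of the change endpoint, and clinical success (a reduction of at least 50%) could not be determined for her.

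**Working it through.** The plan gives no SD, correlation, effect size or power, so it has no figure to reproduce.

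**Inputs.** From the documents: 50 per Group B arm; six items scored 0 to 3, so a maximum of 18; entry score at least 4. Assumed: correlation ρ between baseline and TOC of 0.2 to 0.4; r = SD(TOC)/SD(baseline) of 0.75 to 1.25; baseline SD of 2.5 to 3.5 points. For the MITT population, study 306 retained 188/298 = 63.1%, or about 31 of 50 per arm. That was a different population, so this is a sensitivity value only.

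**1. Scale.** Change equals the TOC score minus baseline. With baseline in the model, switching the outcome from TOC score to change lowers the baseline coefficient by 1 and leaves the treatment coefficient as it was. The two ANCOVAs therefore give one identical treatment effect.

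**2. Gap between the two t-tests.** Their estimates differ by exactly the difference in baseline means between arms. Its 95% range is ±1.96 × SD × √(2/m), with m subjects per arm:

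| Baseline SD | m = 50 | m = 31 |
|---|---|---|
| 2.5 | ±0.98 | ±1.24 |
| 3.0 | ±1.18 | ±1.49 |
| 3.5 | ±1.37 | ±1.74 |

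For scale, clinical improvement is defined as a score of 1 or 2.

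**3. Variance ratios.** ANCOVA/observed = 1 − ρ². ANCOVA/change = r²(1 − ρ²)/(1 + r² − 2ρr).

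| ρ | vs observed | vs change, r = 0.75 | r = 1 | r = 1.25 |
|---|---|---|---|---|
| 0.2 | 0.96 | 0.43 | 0.60 | 0.73 |
| 0.3 | 0.91 | 0.46 | 0.65 | 0.78 |
| 0.4 | 0.84 | 0.49 | 0.70 | 0.84 |

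Estimating the slope multiplies the ANCOVA variance by (n − 3)/(n − 4): 97/96 = 1.010 at n = 100 and 59/58 = 1.017 at n = 62. The observed-score ratio then runs from 0.97 to 0.85 and from 0.98 to 0.85 respectively.

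**4. Power, for illustration.** Take an assumed true difference of 0.5 SD, 50 per arm and r = 1. Power is Φ(0.5/√(2f/50) − 1.96), where f is the variance relative to the observed-score test. At ρ = 0.3, f is 1 for the observed score, 1.4 for change and 0.91 for ANCOVA, giving power of 0.71, 0.56 and 0.75.

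**5. Floor at zero.** Many TOC scores will be 0, so the formulas were checked by simulation with 50 per arm and 4,000 trials per setting. With the entry rule applied, 35% to 63% of TOC scores at zero and ρ of 0.21 to 0.48, ANCOVA/observed was 0.79 to 0.96 and ANCOVA/change 0.40 to 0.78. In a second simulation with 40% to 63% cured and no true difference, ANCOVA type I error was 0.047 to 0.053.

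**6. Site-stratified test of cure (side point).** A site with subjects in only one arm contributes nothing. The information kept is Σ(n₁ₖn₀ₖ/nₖ)/(n/4) over sites k. Site numbers are not in the documents. With 10, 20 or 30 assumed sites and random site membership, the loss is 9%, 19% or 28% at n = 100, and 15%, 30% or 41% at n = 62. The conclusion below does not rest on these figures.

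**The case against.** The natural reading of SAP 6.4.1.2 may be that both summarised quantities are tested, and the secondary endpoint does name change at TOC and FU. Mock tables in a separate document may fix scale and visit. On that reading nobody picks a test after seeing results. But the plan would then report two unadjusted p-values per visit for one question, still without a baseline covariate.

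The gain rests on assumed correlations. Against the observed-score test it is modest, a 2% to 3% saving at ρ = 0.2 after the slope penalty; the large saving applies only against the change score. This stands.

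The consequence is limited. The study is exploratory and unpowered, the t-test between randomised arms is valid, and the comparison of the primary endpoint uses Fisher's exact test. This stands too.

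ANCOVA does not choose a visit, remove the floor at zero, or say what to do with a missing TOC score. Protocol 18.4 counts such a subject as a failure but gives no number for a continuous outcome. Scores taken after additional antifungal therapy are also unaddressed. Naming TOC answers the first of these; the rest need their own sentences.

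The baseline gap arises only where times are missing, and the CRF that would show whether times are recorded is not available here. The rule should not depend on it. The site-stratified test is already presented as additional, so labelling it supportive changes little.

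**Conclusion.** The point holds as a matter of efficiency and prespecification, not validity. It should be fixed before database lock, but it does not threaten the primary comparison. The omission of scale, visit and covariate is plain from the text and needs no assumption. In large samples with 1:1 allocation, ANCOVA is never less precise than either t-test; in finite samples the cost is about 1% to 2% of variance when ρ is near zero. Under ρ of 0.2 to 0.4, the variance saving is about 4% to 16% against an observed-score test before the slope penalty. It is 30% to 40% against a change-score test with equal SDs, or 16% to 57% if the SD ratio runs from 0.75 to 1.25. The ambiguity itself is worth about ±1.0 to ±1.4 points between the two possible estimates at 50 per arm, given a baseline SD of 2.5 to 3.5. The baseline definition needs repair whichever test is used.

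**What to change.** In SAP 6.4.1.2, replace the t-test sentence with wording such as:

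> TOC composite VSS will be compared between Group B 3 days and Group B 7 days by ANCOVA with arm and baseline composite VSS as terms, using robust standard errors. The adjusted mean difference and its 95% CI will be reported.

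State alongside it how a missing TOC score, and a score recorded after additional antifungal therapy, enter this analysis.

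In SAP 6.1.1, define the baseline composite as the Screening sign scores plus the last symptom scores before the first dose. Where times are missing, count same-day assessments scheduled before dosing as pre-dose.

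Keep later visits descriptive: Cycle 2 is open to subjects with insufficient improvement "as evaluated at the TOC visit or at the FU EOT+14 visits", so scores after TOC may reflect further treatment. Keep Fisher's exact test for cure, label the site-stratified test supportive, and fix a rule for pooling small sites before database lock.

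The cost is SAP wording only. The ratings are already scheduled for every subject, and neither visits nor sample size change.
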